**Table 4: ICONIC WP3 Feasibility screening and data collection schedule**

	Completed by	Storage	Pre-consent	Consent	Baseline	6-month follow-up	Ongoing or during intervention
Care homes and workers screened for eligibility	RT	DSH	x				
Care workers consent form	CW / RT	LC / DB		x			
Care workers socio-demographic form	C / RT / CSO	DSH			x		
Service users screened for eligibility	CW	DSH	x				
Service users consent form	SU / RT	LC / DB		x			
Service users socio-demographic and baseline questionnaire	RT / SU / CW	LC / DB			x		
aDIALOG+ app data	SU / CW	ET					x
Video/audio recordings of sessions and checklists	SU / CW	DSH					x
Participant withdrawal CRF	RT / CW / SU	LC / DB					x
SAE CRF	RT / CW / SU	LC / DB					x
Service user 6-month follow up questionnaire	RT / SU / CW	LC / DB				x	

Focus group / interview audio recordings and transcripts	SU / CW / RT / TC	DSH				x	
NoMAD questionnaires	CW / RT	DSH				x	
Treatment costs data	CW / RT	DSH				x	
Key: CW = care worker; DB = database; DSH = data safe haven; ET = encrypted tablet; LC = (locked cabinet on ELFT property); RT = research team; SU = service user; TC = transcription company							

For work package 1a, service users and participant carers will receive a £20 shopping voucher for participating in the interview/focus group following the 6-week intervention period to thank them for their time, and service users will also receive a £20 voucher after taking part in the psychometric testing in work package 1b. For work packages 2 and 3, service users, participant carers and care workers will receive a £20 shopping voucher for completing qualitative interviews, and service users will receive £20 after completing the baseline assessment and £20 prior to the 6-month follow-up assessments to thank them for their time. Participant carers and care workers will also receive £20 following completion of the baseline assessment and prior to the 6-month follow-up assessments.

### Data Storage and Analysis

Data from consenting participants will be collected either on paper (and later inputted) or directly inputted into a password protected database by either CSOs, research assistants or the research team from study visits with participants, or by participating clinicians and care workers from NHS/Social Care Service records / clinical notes. Access to study data will be restricted to the research team who are based within the NHS and Queen Mary University of London and use NHS or university laptops and computers. The app supporting the aDIALOG+ intervention will automatically store usage data (such as number of log ins, clicks and time spent on the software, etc), domain ratings and goals set, but does not collect any identifiable information about the patients it is used with. Such usage data is created and stored automatically by the software on the specific encrypted tablet being used. Data from here will be safely transferred to Queen Mary University of London at the end of the study to allow for proper analysis. Data on the number of sessions attended will be used to assess adherence to the intervention, and we will analyse the mean changes in the scores for each domain on the aDIALOG scale.

Screening / recruitment data, participating professional demographics and data for process evaluation and some treatment costs will be stored in a data safe haven, as will the audio and video recordings of sessions by participating professionals (after being securely transferred to the research team), which will be deleted once the fidelity assessments have been completed. For the qualitative component, audio-files will be transcribed by an approved transcription company, and stored in a data safe haven for analysis by the research team. The original files will be destroyed following transcription and completion of data analysis.

The data generated by the study will be analysed by the Pragmatic Clinical Trials Unit (PCTU), who will be providing methodological, statistical and health economic input, as well

as developing the study database, data management and statistical analysis plans, and ensuring that quality assurance and standard operating procedures are followed. For the qualitative component, audio-files will be transcribed by an approved transcription company, and stored in a data safe haven to be analysed by the research team.

Statistical analysis (work package 1b): We will examine the distribution, variability and mean/median scores for each of the items. In order to assess concurrent and convergent validity, we will examine spearman's correlation between the items relating to subjective quality of life on the aDIALOG scale and the other measures. We will assess test re-test reliability by calculating the intra class correlation coefficient (ICC). Items that show poor distribution, variability and poor test re-test reliability may be removed from the scale. We will measure the internal consistency of the items relating to subjective quality of life and the treatment aspects separately using Cronbach's alpha.

Statistical analysis (WP 2 and WP 3): The feasibility outcomes will be the main focus of analysis and descriptive statistics, with associated measures of precision appropriately accounting for clustering, will be used to assess recruitment and retention, adherence, response rates in completing the outcome measures, demographic and clinical data, and cost data. We will explore changes in the scores of the outcome measures using paired t-tests or non-parametric tests where appropriate. The primary outcome measure of changes in behaviour will be measured using the Aberrant Behaviour Checklist (ABC)- irritability subscale (43). For secondary outcomes we will measure changes in behaviour (Behaviour Problems Inventory- short form) (53), quality of life (WHOQOL Disabilities module) (40), community participation (Guernsey Community Participation and Leisure Assessment – Revised) (44), psychological distress (Clinical Outcomes in Routine Evaluation, 14 item version) (42), psychiatric disorders (Moss Psychiatric Assessment Schedule - Check) (45), global improvement (Clinical Global Impression Scale) (46), health related quality of life (modified version of the EQ-5D-3L for people with ID) (48, 49) and service use (the Client Services Receipt Inventory) (51). The frequencies of adverse and serious adverse events will also be reported.

In order to determine the minimal clinically important difference (MCID) for our primary outcome measure (ABC-I), we will compare changes in the ABC-I before and after aDIALOG+ and this will be linked to improvements in service users', care workers' or clinicians' ratings on the Clinical Global Impression Scale (global improvement measure). A change indicating that the patient is at least a "minimally improved" will be used as the cut-off score to indicate improvement. We will conduct sensitivity analyses to test different assumptions.

Qualitative data will be analysed using framework analysis to identify themes relating to the barriers and facilitators in implementing aDIALOG+ in clinical and care home settings and aspects of the intervention that need to be refined such as training, supervision and number and frequency of sessions. The focus groups/interviews will be audio-recorded and transcribed. We will use NVIVO to analyse the data using framework analysis to identify relevant themes relating to aspects of the intervention that did not work well and require further modifications, which will inform changes to the intervention. We will also ask clinicians and care workers to complete the NoMAD questionnaire (39) for assessing implementation processes from the perspective of professionals directly involved in the work of implementing complex interventions in healthcare.

Statistical analysis will be carried out on pseudo-anonymised data, and therefore personal identifiable data will not be published. For qualitative interviews, we will remove all

identifiable information from interview transcripts prior to analysis. Participants will be identified using a study ID in publications and we will take care not to present a combination of personal information together that could identify the person (e.g. age, gender, ethnicity).

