## **Why DIALOG+ needs to be adapted for people with ID**

DIALOG+ has not been used or evaluated in people with ID. Feedback from service users with ID and clinicians who we have engaged with, have been positive about the potential for DIALOG+ to facilitate improved communication between clinicians and service users. One service user commented "it's important that professionals ask the right questions about what is important to me". DIALOG+ could empower individuals with ID to engage in meaningful conversations, promoting a greater sense of control and agency, potentially leading to improved QoL and fewer behaviours that challenge. However, they emphasised that the existing intervention is not accessible for this population (e.g. language/ response format of the DIALOG scale/ supporting app is too complex and the QoL domains are not all relevant. Evidence from the literature suggests that quality of life domains such as autonomy and rights are important for people with ID but the existing DIALOG scale does not include these domains (26-27).

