### 4.1 Objectives

The principle objectives of these phases of the programme are:

- 1) To pilot the adapted DIALOG quality of life scale and intervention (aDIALOG+) and obtain feedback on what aspects of the intervention (including the aDIALOG scale, supporting app, training and manual) worked well or did not work well and suggestions for improvement.
- 2) To test the psychometric properties of the aDIALOG scale to establish whether the aDIALOG scale is a useful quality of life measure in people with ID.
- 3) To conduct a single arm, uncontrolled, feasibility study of aDIALOG+ delivered by clinicians from community ID services to assess recruitment and retention of service users and clinicians.
- 4) To conduct a single arm, uncontrolled, feasibility study of aDIALOG+ delivered by care workers from care homes (supported living or residential care) for people with ID to assess recruitment and retention of care homes, care workers and service users.

The secondary objectives of these phases of the programme are:

- 1) To examine intervention adherence (number of sessions attended)
- 2) To examine intervention fidelity (whether intervention is delivered as intended)
- 3) To examine completion and changes in clinical outcome measures (behaviour that challenges, quality of life; community participation, psychological distress, psychiatric disorders, health related quality of life).
- 4) To explore acceptability of the intervention amongst service users, clinicians and care workers.
- 5) To examine the feasibility of collecting data on costs and service use.
- 6) To establish the minimal clinically important difference (MCID) for the Aberrant Behaviour Checklist – Irritability scale (primary outcome)

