## 5 STUDY DESIGN AND METHODS OF DATA COLLECTION AND DATA ANALYSIS

### *Intervention*

The current DIALOG+ intervention is a person-centred intervention delivered/supported by a free app and a Progressive Web Application (PWA), enabling its use on electronic devices. It aims to improve the therapeutic effectiveness of routine clinical meetings between patients and clinicians by asking the patient to rate their satisfaction with eight life domains on the DIALOG QoL scale:

- 1) Mental health
- 2) Physical health
- 3) Job situation
- 4) Accommodation
- 5) Leisure activities
- 6) Relationship with partner/family
- 7) Friendships
- 8) Personal safety

and three treatment aspects:

- 1) Medication
- 2) Practical help
- 3) Meetings with professionals

The scale has a seven-point response format from 1 (totally dissatisfied) to 7 (totally satisfied). After the patient rates each domain, they are asked whether additional help is required with that domain. The ratings are summarised and the patient and clinician agree which domains to discuss further, followed by a four-step solution focussed approach to identify the individual's existing resources that can be mobilised to address the concerns:

- 1) Understanding the individual's concerns and previous effective coping strategies
- 2) Looking Forward (what is the best-case scenario and smallest step forward?)
- 3) Exploring Options (what resources are available to the individual, clinician or others in the person's network?)
- 4) Agreeing on Actions (e.g. homework and referrals), which are reviewed at the next meeting.

The app supporting the DIALOG+ intervention will automatically store usage data (such as number of log ins, clicks and time spent on the software, etc), domain ratings and goals set, but does not collect any identifiable information about the patients it is used with.

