### **Co-production work to develop an adapted version of DIALOG+**

Prior to the study, we will hold five workshops with service users, clinicians and care workers in order to develop an adapted version of the DIALOG+ (aDIALOG)+ that will be accessible and suitable for use in people with ID. This may involve changes to the response format and wording of the DIALOG+ QoL scale and four step solution focused approach, as well as updating the Progressive Web Application to make it more accessible and engaging for people with ID. We will modify the training manual and training resources.

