## 2. Work package 1b: testing the psychometric properties of the aDIALOG quality of life scale

Research assistants will arrange a face-to-face meeting or conduct the assessment remotely on Teams or Zoom. We will collect basic socio-demographic data (gender, age, ethnicity, severity of ID, neurodevelopmental conditions, day activities, living arrangements, co-morbid psychiatric and physical illnesses) and we will ask service users to complete the aDIALOG scale and the following measures (in order to assess construct and concurrent validity):

- i. Mini-MANS LD and the WHOQOL Disabilities module (measures of quality of life in people with ID) (40, 41).
- ii. Clinical Outcome in Routine Evaluation- Learning Disability (CORE-LD), 14 item version (measure of psychological distress) (42).

In order to assess test re-test reliability, we will ask service users to complete the aDIALOG scale again on another occasion (ideally 24 hours later but no later than 1 week). This will be carried out face-to-face, online or via telephone.

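### The WP1b validity analysis correlates single aDIALOG items with the comparators and defines no scale score, although objective 2 concerns the scale

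*Protocol*

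**What the plan says.** Section 4.1 of the protocol lists as a principal objective testing the psychometric properties of the aDIALOG scale "to establish whether the aDIALOG scale is a useful quality of life measure in people with ID". Section 2 likewise says that validating the scale will help fill the lack of a sound quality of life measure in this population.

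The only validity analysis is in section 5, Data Storage and Analysis, under statistical analysis for work package 1b. It covers concurrent and convergent validity and reads: "we will examine spearman's correlation between the items relating to subjective quality of life on the aDIALOG scale and the other measures". The same paragraph plans item distributions, test-retest ICC, possible removal of poorly performing items, and Cronbach's alpha computed separately for the subjective quality of life items and the treatment aspects.

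The WP1b data collection section names three comparators: two quality of life measures (Mini-MANS-LD and WHOQOL-DIS) and one measure of psychological distress (CORE-LD). It gives their purpose as construct and concurrent validity, whereas the analysis paragraph speaks of concurrent and convergent validity.

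No aDIALOG total, mean or subscale score is defined anywhere in the protocol. Table 2 lists item scores only, and the planned change analyses for the feasibility studies are domain by domain.

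**The concern.** The unit in the analysis does not match the unit in the objective. A claim that a scale measures quality of life rests on how the scale's score relates to other measures of quality of life. The planned correlations describe single items instead. An item has more measurement error and narrower content than the mean of the items, so its correlation with a multi-item comparator is typically smaller. Computing alpha for the subjective items presupposes that they belong together as a set, yet no stated analysis tests the validity of their combination.

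At stake is the answer to a principal objective. A set of modest item coefficients could make a sound scale look weak, and the figure that readers would need, the scale-level coefficient with its precision, would not be among the planned results.

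**Working it through.** **The plan's own figure.** There is none to reproduce. The protocol gives no target correlation, precision or justification for the 120 participants in WP1b. The 18% half-width in section 7.2.1 belongs to the feasibility work.

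**Inputs from the protocol**
- n = 120 (section 7.2.1).
- Three comparators: two of quality of life, one of distress (section 5, Data Collection, WP1b).
- Item count: the existing scale asks people to "rate their satisfaction with eight life domains on the DIALOG QoL scale", so k = 8 is used. The aDIALOG count is not stated.

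**Assumptions**
- Cronbach's alpha 0.70 to 0.85.
- True scale-comparator correlation 0.60, with 0.50 and 0.70 as the range.
- Parallel items: equal inter-item correlations and equal correlations with the comparator.

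**Step 1: from alpha to the mean inter-item correlation.** r_ii = alpha / (k − (k − 1) × alpha).
- alpha 0.70: 0.70 / (8 − 4.90) = 0.226
- alpha 0.80: 0.80 / (8 − 5.60) = 0.333
- alpha 0.85: 0.85 / (8 − 5.95) = 0.415

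**Step 2: ratio of item to scale coefficient.** r_item / R_scale = sqrt((1 + (k − 1) × r_ii) / k).

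| alpha | ratio | R = 0.50 | R = 0.60 | R = 0.70 |
|---|---|---|---|---|
| 0.70 | 0.57 | 0.28 | 0.34 | 0.40 |
| 0.80 | 0.65 | 0.32 | 0.39 | 0.45 |
| 0.85 | 0.70 | 0.35 | 0.42 | 0.49 |

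With ten items (an assumption, should domains be added) the ratio falls to 0.52 at alpha 0.70 and 0.65 at alpha 0.85. A scale value of 0.60 would then appear as 0.31 to 0.39.

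**Step 3: simulation with ordinal items.** 3000 samples of n = 120 were drawn, with eight equally valid 7-point items skewed towards satisfied, one comparator and a true scale correlation of 0.60.

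| alpha | lowest item (average) | highest item (average) | mean score (average) |
|---|---|---|---|
| 0.70 | 0.21 | 0.43 | 0.57 |
| 0.80 | 0.26 | 0.46 | 0.57 |
| 0.85 | 0.30 | 0.48 | 0.58 |

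So equally valid items differ noticeably by chance, and even the highest of the eight averages below the coefficient for the mean score.

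**Step 4: precision of the scale-level coefficient.** Take the Fisher transform with Spearman variance (1 + r²/2) / (n − 3). For r = 0.60 the standard error is sqrt(1.18 / 117) = 0.100. On the transformed scale the interval is 0.693 ± 0.197, which gives 0.46 to 0.71. The same formula gives 0.34 to 0.63 for r = 0.50 and 0.58 to 0.79 for r = 0.70.

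**The case against.** The strongest reply is that the phrase can mean the subjective items taken together. The Cronbach's alpha sentence uses nearly the same words for an item set, and where the paragraph clearly means item by item, in describing distributions, it refers to each item. This reading is possible but not the natural one: a correlation needs a score, and the protocol names none. If it is what the sponsor intends, the wording still needs to say so.

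Item-level evidence also has a proper use. The intervention works domain by domain, and so do the planned change analyses. That is a reason to keep item correlations, not a reason to leave out the scale-level one. It is also true that nothing is lost: item scores and all comparators are collected, so a mean score can be computed later. This limits the harm but does not correct the stated analysis.

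Several stronger readings are tempting and are not supported:

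- **A fixed number of coefficients.** Eight items by three measures would give 24, but eight is the count for the existing scale. On the planned adaptation the protocol says "This may involve changes to the response format and wording of the DIALOG+ QoL scale", the background notes that "quality of life domains such as autonomy and rights are important for people with ID" and that the existing scale lacks them, and items may be dropped after testing.
- **The plan could give opposite answers, with a flattering item quoted as proof.** No threshold is set, so nothing passes or fails. In the simulation even the highest item coefficient averages below the scale's, and nothing in the protocol suggests selective reporting.
- **Quality of life and distress comparators are mixed together.** The data collection section lists them separately with their constructs. Only the link from comparator to type of validity is left loose in the analysis paragraph.
- **The protocol fails by naming no deciding comparator or cut-off.** A protocol commonly leaves these to the statistical analysis plan, which section 5 says the trials unit will develop.

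**Conclusion.** The point holds as a mismatch between unit and claim. The analysis paragraph names items as the unit for validity, no aDIALOG score is defined, and objective 2 concerns the scale. Read literally, the validity of the combined score goes unestimated, and the coefficients reported in its place would be roughly 30% to 43% smaller.

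That size rests on eight parallel items and alpha of 0.70 to 0.85, none of which the protocol states. With items that are not parallel, a single item could match or exceed the scale on a closely related comparator; the weakening then describes the average item.

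A reader might infer that WP1b cannot meet its objective. The document does not support that. WP1b is described as exploratory, the objective covers psychometric properties in general, and retest reliability and internal consistency are also planned. The defect is confined to the validity part and can be corrected from the data already due to be collected.

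**What to change.** In the WP1b analysis paragraph, and in the statistical analysis plan to match:

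1. Define the aDIALOG subjective quality of life score as the mean of the retained subjective items.
2. For concurrent and convergent validity, give the Spearman correlation with 95% confidence interval between that score and each quality of life measure, Mini-MANS-LD and WHOQOL-DIS.
3. For construct validity, give the same correlation with CORE-LD and state the expected direction in advance.
4. Keep the item-by-measure correlations as supporting description.
5. Use the same validity terms in the data collection and analysis sections.

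The cost is a few sentences. No additional participants, measures or visits are needed. Choosing one deciding comparator or setting a threshold is optional and can be left to the statistical analysis plan.

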#### vi. Global improvement

We will assess whether there are changes in behaviour and functioning as a result of the intervention (at 6 months) using a modified version of the Clinical Global Impressions Scale

(CGI) (46). The CGI global improvement measure (CGI-I) will be rated by the clinician (or care worker) delivering aDIALOG+, the service user and also the participant carer. The scale is rated from 1 (very much improved) to 7 (very much worse).

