## **7.2 Sampling**

### **7.2.1 Size of Sample**

- Work package 1a: 5 clinicians, 5 care workers and 20 service users.
- Work package 1b: 120 service users.
- Work package 2: 8-12 clinicians, 30 service users, and 10 participant carers.
- Work package 3: 10 care homes and their care workers (3-5 care workers in each care home, approx. 40 care workers). 3-5 service users in each care home (approximately 40 service users).

Total number of participants: clinicians - 17; care workers- 45; service users- 210; participant carers- 10.

For the feasibility study there is no formal sample size calculation but the sample size would need to be sufficient in order to estimate our main parameters of interest (recruitment and retention rates) and the precision of these estimates, allowing for the clustered nature of the data (Assuming an ICC of 0.04). If we anticipate a recruitment and retention rate of 75%, 12 clinicians, and 30 service users, would allow us to estimate 95% Confidence Intervals for recruitment and retention rates with a half width of 18%.

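### Change in ABC-Irritability and the secondary outcomes is analysed with paired tests that ignore clustering by clinician or care home; the error is modest and cheap to correct

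*Protocol*

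**What the plan says.** In the Protocol, Data Storage and Analysis, the paragraph on WP2 and WP3 handles two groups of results differently.

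- **Feasibility results.** The plan is that "descriptive statistics, with associated measures of precision appropriately accounting for clustering, will be used to assess recruitment and retention". The same provision extends to adherence, response rates, demographic and clinical data, and costs.
- **Clinical outcomes.** The next sentence reads "We will explore changes in the scores of the outcome measures using paired t-tests or non-parametric tests where appropriate". No clustering term appears. The sentences that follow name the outcomes, beginning with "The primary outcome measure of changes in behaviour will be measured using the Aberrant Behaviour Checklist (ABC)- irritability subscale", and then the secondary measures.

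Section 7.2.1 (Size of Sample) recognises the structure of the data, "allowing for the clustered nature of the data (Assuming an ICC of 0.04", and gives a precision figure for WP2: "If we anticipate a recruitment and retention rate of 75%, 12 clinicians, and 30 service users" are said to give "95% Confidence Intervals for recruitment and retention rates with a half width of 18" per cent. WP2 has 8-12 clinicians and 30 service users. WP3 has 10 care homes and about 40 service users, 3-5 per home. The only sensitivity analyses mentioned concern the minimal clinically important difference, not clustering.

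**The concern.** A paired t-test or signed-rank test treats each service user's change as an independent observation. Service users here share a clinician in WP2 or a care home in WP3, and in WP3 delivery may be shared across a team of care workers. If changes are positively correlated within a clinician or home, an independence-based test gives standard errors that are too small and p-values that are too low.

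The protocol is also inconsistent with itself: the provision "with associated measures of precision appropriately accounting for clustering" stops one sentence before the outcome labelled primary. Because the protocol names the test, this is not a detail left open for a statistical analysis plan; a plan using a clustered method would depart from the text. At stake is the stated uncertainty around change in ABC-Irritability and the other measures. Examining such change is a secondary objective (section 4.1).

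**Working it through.** **Inputs.** From section 7.2.1: ICC 0.04 (stated for recruitment and retention only), anticipated rate 75%, WP2 with n = 30 and k = 8 or 12 clinicians, WP3 with n = 40 and k = 10 homes. Mean cluster size m = n/k is 2.5, 3.75 and 4. Not in the document, so assumed: a two-sided 5% level, and any ICC for change scores.

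**Step 1. Reproduce the protocol's own figure.** Design effect DE = 1 + (m − 1) × ICC. For 12 clinicians, DE = 1 + 1.5 × 0.04 = 1.06. Half width = t(11) × √(0.75 × 0.25 / 30 × 1.06) = 2.201 × 0.0814 = 0.179, or 18%. A normal quantile without the design effect gives 0.155, and with it 0.160. So the stated 18% is matched by an approach that uses both the design effect and degrees of freedom based on clinicians.

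**Step 2. Apply the same design effect to change scores at ICC 0.04.** The correct standard error is √DE times the naive one. The actual level of a nominal 5% test is approximately 2 × [1 − Φ(1.96/√DE)].

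| Setting | DE | √DE | Actual level |
|---|---|---|---|
| WP2, 12 clinicians | 1.06 | 1.030 | 5.7% |
| WP2, 8 clinicians | 1.11 | 1.054 | 6.3% |
| WP3, 10 homes | 1.12 | 1.058 | 6.4% |

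Simulation of the paired t-test with 10 homes of 4 gives 6.3%, so 5.7-6.3% is a fair summary. If only 75% of the WP3 sample is retained (m = 3), DE is 1.08 and the level about 5.9%.

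**Step 3. Other ICC values (assumptions).** In WP3 at 0.15, DE = 1 + 3 × 0.15 = 1.45, √DE = 1.204, and the level is 10.4% by formula and by simulation. At 0.10 it is 8.6%, and at 0.20 about 12%.

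**Step 4. Width of a corrected interval at ICC 0.04.** With k − 1 degrees of freedom, the ratio to the paired t interval is √DE × t(k − 1)/t(n − 1).

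- WP2, 12 clinicians: 1.030 × 2.201/2.045 = 1.108
- WP2, 8 clinicians: 1.054 × 2.365/2.045 = 1.218
- WP3: 1.058 × 2.262/2.023 = 1.184

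In WP3 the factor 1.184 splits into 1.058 for the design effect and 1.118 for degrees of freedom. Only the first part is under-coverage of the planned test. An interval truly too narrow by a factor of 1.184 would imply a level of 2 × [1 − Φ(1.96/1.184)], about 9.8%, not 6.3%.

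**Step 5. What is not affected.** Unless cluster size is related to change, the sample mean change is unbiased. With equal clusters, the expected sample variance is 1 − (m − 1) × ICC/(n − 1) of the true value. In WP3 that is 0.997 at ICC 0.04 and 0.988 at 0.15.

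**The case against.** The strongest reply is that little hangs on this. The protocol makes feasibility its main analysis, says only that changes will be explored, declares the design single-arm and uncontrolled, and ties no decision to these p-values. The ICC of 0.04 is not stated for change scores. Stable differences between homes cancel in within-person change, so the relevant ICC could be lower. Shared raters are not established either: in WP2 participant carers, not the clinician, complete ABC-Irritability; in WP3 the informant is each person's main key worker, who may or may not be shared; and several measures are completed with the service user. All of this stands and limits the size of the point. It does not remove it, because the test named is the wrong one for data that the protocol itself calls clustered.

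Three stronger readings are tempting but unsupported.

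- **That the planned intervals are 18-22% too narrow.** Steps 2 and 4 show the shortfall is about 3-6% at ICC 0.04; the rest is the cost of cluster-level degrees of freedom.
- **That wrong change estimates and standard deviations would feed the next trial.** The protocol states no such use, and step 5 shows that these quantities barely move.
- **That the tests would manufacture a treatment effect.** Regression to the mean in people selected for a recent incident is a limit of any single-arm study, and a clustered model does not cure it. The wording "changes in behaviour and functioning as a result of the intervention (at 6 months" belongs to the global improvement rating, not to the paired tests. Whether to report p-values at all is a matter of preference.

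**Conclusion.** The point holds as a modest analysis error. The protocol fixes independence-based tests for change in the primary and secondary outcomes immediately after requiring clustered precision for the feasibility results. If the ICC of change is 0.04, standard errors are understated by about 3-6% and a nominal 5% test runs at 5.7-6.3%. If it were 0.15 in WP3, which is an assumption without support in the document, the test would run at about 10%. The direction depends only on the within-cluster correlation of change being positive; the size depends on an ICC that the protocol does not give. It concerns an exploratory secondary analysis and leaves the feasibility conclusions untouched.

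**What to change.** Replace the sentence on paired and non-parametric tests in Data Storage and Analysis. State that mean change from baseline to 6 months will be reported with a 95% confidence interval, separately for WP2 and WP3, accounting for clustering by clinician (WP2) or care home (WP3). Two methods would serve:

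- a mixed model for change with a random intercept for clinician or home and small-sample degrees of freedom;
- a t interval on cluster means.

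Name the second at least as a fallback. With 10 homes of 4 and ICC 0.04, the between-home variance is estimated at zero or below when the ratio of mean squares falls under 1. That has probability P(F(9, 30) < 0.96/1.12 = 0.857), about 43%, and the mixed model would then move towards the unclustered result. Report the estimated ICC of change as well.

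The cost is one changed sentence and some analysis work, with no new data or participants. Reported intervals would be about 11-22% wider than the paired t interval at ICC 0.04 if cluster-level degrees of freedom are used.
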